8.0 Statistical Considerations

This is a phase II study with a primary objective of assessing the safety of Fludarabine, and Busulfan as preparative regimens for allogeneic stem cell transplantation in patients with Myelofibrosis and MDS. Patients enrolled in the study will be younger than 75 years of age and must have an HLA matched or at least a 9/10 antigen matched related or unrelated donor. The major reason for treatment failure in these patients is transplant related mortality. Therefore, in order to assess the primary objective of safety, the primary outcome measure will be the rate of non-relapse mortality (NRM) at 100 days. We will define non-relapse mortality as any death not attributable to disease recurrence. The cumulative incidence rates of NRM ranged from 27%-48% in three studies of younger patients with this disease. The NRM rate is expected to be much higher in this mostly older group of patients with advance myelofibrosis we are proposing to treat because NRM increases with age and coexisting medical illnesses. Therefore, the goal of the trial is to achieve better than a 30% NRM rate at 100 days post transplant with this treatment regimen. The proposed trial will evaluate the role of allogeneic stem cell transplantation a using reduced-intensity conditioning regimen of fludarabine and busulfan. These patients will receive 4 days of the Fludarabine regimen and 2 days of the Busulfan regimen. The maximum total sample size for this trial was originally 30 patients. It was increased in July 2009 to 60 patients. As of September 2011, 49 patients have been enrolled, and we now plan to increase enrollment to 110 patients. We expect to accrue 20 patients a year for a total of 3 years. The goal of the trial is to achieve better than a 30% NRM rate at 100 days post transplant. We will stop the trial if we have evidence that the NRM rate is higher than targeted.

The method of Thall and Simon will be employed to perform interim safety monitoring. As of September 2011, a total of 49 patients have been enrolled, of which 45 have been evaluated for NRM at day 100. Monitoring has proceeded according to the original stopping rule with no need for early study termination. For the remaining 65 patients, we will employ the following monitoring rule. The trial will be stopped early if:

$$\Pr[\theta \in E, D > 0.30 | \text{data}] > 0.90$$

That is, given the outcomes from the patients who have already been evaluated, if we determine that there is greater than a 90% chance that the NRM rate is 30% or more, we will stop the trial. We assume a Beta(0.6, 1.4) prior distribution for the rate of non-relapse mortality. Because 45 patients have been evaluated to date, stopping boundaries corresponding to the above probability criterion start at the 45th patient. We will terminate the trial if:

$$(\# \text{ of non-relapse mortalities}) / (\# \text{ patients evaluated})$$

$\geq 18/45, 19/47, 19/48, 20/50, 20/51, 21/53, 21/54, 22/56, 22/57, 23/59, 23/60,$
 $24/62, 24/63, 25/65, 26/67, 26/68, 27/70, 27/71, 28/73, 28/74, 29/76, 29/77, 30/79,$
 $30/80, 31/82, 31/83, 32/85, 32/86, 33/88, 33/89, 34/91, 34/92, 35/94, 35/95, 36/97,$
 $36/98, 37/100, 37/101, 38/103, 38/104, 39/106, 39/107, \text{ or } 40/109$

It should be noted that these boundaries are unconditional on the fact that 43/45 evaluable patients to date did not experience NRM. Thus, the first several stopping boundaries are impossible to meet, but they are listed for completeness. If each of the subsequent patients experience NRM, the first stopping boundary that could potentially stop the study is if 27/70 evaluable patients experience NRM.

Accrual will not be suspended while waiting to evaluate the 100-day NRM rate.

The operating characteristics of this study design are shown in the following table. As was the case above, it should again be noted that the listed stopping probabilities and sample size quantiles are unconditional upon the observed data.

Table 2. Operating Characteristics for Stopping Rule

Clinical Scenario	Early Stopping Probability	Sample Size: 25th, 50th, 75th percentiles		
Non-relapse mortality rate is 0.20	0.002	110	110	110
Non-relapse mortality rate is 0.25	0.04	110	110	110
Non-relapse mortality rate is 0.30	0.22	110	110	110
Non-relapse mortality rate is 0.35	0.59	45	80	110
Non-relapse mortality rate is 0.40	0.89	45	45	68
Non-relapse mortality rate is 0.45	1.00	45	45	45

Secondary Endpoints

Efficacy endpoints such as time to engraftment, complete remission (CR), progression-free survival (PFS), and overall survival (OS) will be evaluated after 3-years of follow-up. We will estimate each of these efficacy endpoints with the Kaplan-Meier estimators. In addition, we will report each of the estimates along with their corresponding two-sided 95% confidence intervals. We will use Cox proportional hazards regression analysis to assess the association between the above survival parameters and clinical and demographic covariates of interest. We will use logistic regression to assess the association between clinical response (CR/PR vs. SD/PD) and the same covariates.

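### From 66 evaluable patients on, 15 printed stopping boundaries for NRM sit one patient later than the stated posterior criterion requires; the first reachable stop is 26/69 under the criterion and 27/70 under the list

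*Combined protocol and SAP*

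**What the plan says.** All of the relevant text is in section 8.0, Statistical Considerations, of the combined protocol and SAP.

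- Method: "The method of Thall and Simon will be employed to perform interim safety monitoring".
- Criterion: the displayed formula requires a posterior probability above 0.90 that NRM exceeds 0.30. The prose restates it: "if we determine that there is greater than a 90% chance that the NRM rate is 30% or more, we will stop the trial". In both places 30% is a fixed number.
- Prior: "We assume a Beta(0.6, 1.4) prior distribution for the rate of non-relapse mortality".
- Link between criterion and list: "stopping boundaries corresponding to the above probability criterion start at the 45th patient". The list has 43 fractions, from 18/45 to 40/109. Around the place where it changes pattern it reads "25/65, 26/67, 26/68, 27/70, 27/71".
- Consequence given the data so far (2 events in 45 evaluable patients): "the first stopping boundary that could potentially stop the study is if 27/70 evaluable patients experience NRM".
- Table 2 gives operating characteristics, with the caveat that "the listed stopping probabilities and sample size quantiles are unconditional upon the observed data".

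**The concern.** The section gives everything needed to regenerate the list: threshold, cut-off, prior and starting point. The regenerated list should therefore equal the printed one. It does so up to 65 patients, and then the pattern of skipped denominators shifts. Up to 63 the printed denominators skip 46, 49, 52 and so on to 64; after 65 they skip 66, 69, 72 and so on to 108.

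This is the stopping rule for the primary safety endpoint, and a stopping boundary is an exact integer rule. If the list and the criterion differ, a monitor who computes the posterior and a monitor who reads the list can reach opposite decisions on the same data.

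**Working it through.** **Inputs (all from section 8.0).** Prior Beta(0.6, 1.4); fixed threshold 0.30; cut-off 0.90; monitoring from n = 45; maximum 110 patients; 2 events in 45 to date.

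**Formula.** With x events in n patients the posterior is Beta(0.6 + x, 1.4 + n − x). The boundary at n is the smallest x with Pr(θ > 0.30) > 0.90.

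**Step 1: the printed fractions.** All 43 are the exact minimum at their own n. For example, 18/45 gives 0.914 and 17/45 gives 0.856.

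**Step 2: the gaps up to n = 65.** At n = 46, 18 events give 0.897, so the minimum is 19. Nobody can be at 19/46 without having had at least 18/45, which already stops the trial. Leaving out n = 46 is therefore correct. The same holds at 49, 52, 55, 58, 61 and 64, so the list is complete to n = 65.

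**Step 3: the gaps from n = 66.** 25/66 gives 0.9069, which meets the criterion. It can be reached from 24/65 (0.875, no stop) by one further event. It is not listed; 26/67 (0.932) is printed instead. The pattern repeats every three patients:

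| Meets criterion, not listed | Posterior | Printed instead | Posterior |
|---|---|---|---|
| 25/66 | 0.9069 | 26/67 | 0.9319 |
| 26/69 | 0.9064 | 27/70 | 0.9311 |
| 27/72 | 0.9061 | 28/73 | 0.9305 |
| … | 0.906–0.908 | … | 0.928–0.930 |
| 39/108 | 0.9080 | 40/109 | 0.9283 |

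There are 15 such pairs. Once the omitted points are included, the 15 printed neighbours can no longer be newly crossed. Both lists then have 43 entries, so this is a displacement and not a shortened list.

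**Step 4: first reachable stop.** From 2/45, if every later patient has an event, the count is 25 at n = 68 (2 + 23; boundary 26, continue) and 26 at n = 69 (2 + 24; posterior 0.906, stop). The list stops first at 27/70. If the 70th patient has no event, 26/70 gives 0.892 and the printed rule continues, although the criterion had already called for a stop.

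**Step 5: operating characteristics.** Exact binomial recursion, unconditional, with 25th/50th/75th sample-size percentiles:

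| True NRM | Table 2 | Printed list | Stated criterion |
|---|---|---|---|
| 0.20 | 0.002 | 0.003 | 0.003 |
| 0.25 | 0.04 | 0.040 | 0.042 |
| 0.30 | 0.22 | 0.223 | 0.236 |
| 0.35 | 0.59; 45/80/110 | 0.590; 45/80/110 | 0.610; 45/77/110 |
| 0.40 | 0.89; 45/45/68 | 0.888; 45/45/68 | 0.898; 45/45/66 |
| 0.45 | 1.00 | 0.986 | 0.988 |

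Table 2 follows the printed list in its percentiles and middle rows. Its 0.002 and 1.00 match neither version on rounding (the list gives 0.0029 and 0.986).

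**Step 6: possible source of the list.** No single cut-off with a fixed 0.30 and this prior can produce it: 24/63 is listed at 0.9074, while 39/108 is omitted at the higher value 0.9080. Replacing the fixed 0.30 by a random standard rate distributed Beta(300, 700) reproduces the whole list (25/66 = 0.8997, 26/69 = 0.8990, 39/108 = 0.8965, 27/70 = 0.9242). That distribution is an assumption tested here and is not in the documents. It is also not unique: a mean of 0.30 with prior size 950, or a fixed rate of 0.3022 to 0.3024, fits equally well.

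**The case against.** The strongest reply is that no printed fraction is wrong at its own n, and that section 8.0 never says the criterion is applied after every patient. If decisions are taken only at the listed denominators, the list, the 27/70 sentence and the main rows of Table 2 agree, and anyone using the list alone has one answer.

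The first part stands: the fault lies in what is omitted. The second part does not hold. The prose criterion is not restricted to particular denominators, and every gap through n = 65 is exactly a point that cannot be newly crossed when the rule is checked after each patient. Carrying the last boundary forward across gaps does not help either: 26/69 would then stop the trial, against the 27/70 sentence, and 18/46 would stop it at a posterior of only 0.897.

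It is also fair to say that the practical effect is slight. Starting from 2/45, the probability of stopping (list against criterion) is 0.0018 against 0.0024 if NRM in later patients is 0.40, 0.096 against 0.110 at 0.50, and 0.617 against 0.644 at 0.60. Accrual is not suspended, and at 20 patients a year about 20 × 100/365 = 5.5 patients are inside the 100-day window at any time, which exceeds a one-patient shift. This limits the importance of the point but does not remove the contradiction.

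**Conclusion.** The point holds. As written, either the criterion or the list is wrong, and they give different decisions at 15 counts from n = 66 to n = 108. Over the Table 2 scenarios the difference in early-stopping probability is at most about 0.02, so this is not a claim that the trial is materially less safe. The result assumes that the criterion is applied after each evaluable patient and that 0.30 is the fixed number the text gives. Which of the two was intended cannot be settled from the documents. It should be corrected because the primary safety rule ought to have a single reading.

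**What to change.** Reconcile the criterion and the list in one of two ways.

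1. **If the fixed 0.30 is intended**, replace the 15 displaced points: 26/67 by 25/66, 27/70 by 26/69, 28/73 by 27/72, 29/76 by 28/75, 30/79 by 29/78, 31/82 by 30/81, 32/85 by 31/84, 33/88 by 32/87, 34/91 by 33/90, 35/94 by 34/93, 36/97 by 35/96, 37/100 by 36/99, 38/103 by 37/102, 39/106 by 38/105 and 40/109 by 39/108. Change 27/70 to 26/69 in the sentence on the first possible stop, and recompute Table 2.
2. **If a random standard rate was used**, state its distribution and rewrite the criterion to match. The list and the 27/70 sentence then stand.

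In either case, say that the rule is checked after each evaluable patient, and recheck the Table 2 entries 0.002 and 1.00. Optionally, add stopping probabilities conditional on 2/45. Their absence is not an error, since the plan discloses that Table 2 is unconditional.

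The cost is text in section 8.0 only, with no extra patients, data or visits. The first option raises the stopping probability at a true NRM of 0.25 from 0.040 to 0.042.

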A special problem area is the treatment of older or debilitated patients. Guardiola published a series of 55 patients demonstrating inferior results for older patients: Five year survival of 14% in patients older than 45 years compared to the 5 year survival of 62% in younger patients (12). These inferior results in older patients and patients with comorbidity who comprise majority of patients with this disease make myeloablative transplantation a promising but not suitable therapy most patients with myelofibrosis.

Another approach would be to use a reduced intensity or a nonmyeloablative conditioning regimen, which have been reported to extend allogeneic transplant to older patients and patients with other co-morbid medical conditions. Others and we have shown that reduced intensity stem cell transplantation can be safely utilized in older patients and those with comorbidities in other hematological malignancies (17-22). Rondelli et al and Kroger et al have reported encouraging data in multi institutional studies of reduced intensity transplantation in older patients with myelofibrosis as detailed in the table 1(15,16). In these retrospective studies with a median age of 54 years, a non-relapse mortality of 10%-16% and 3 year overall survival of 84%-85% was reported. We wish to prospectively evaluate the role of allogeneic stem cell transplantation using reduced intensity conditioning regimen of fludarabine and busulfan.

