6.0 Evaluation During Study

Evaluations for this study (6.1-6.5) are considered standard practice in BMT and should be done around 1, 3, 6, 9, 12, 18 and 24 months post transplantation. If clinically indicated these studies may be done at other time points to evaluate for potential relapse of the underlying malignancy, which can replace the nearest planned time points. After two years patient will be seen annually or information about patient's condition will be obtained by a telephone call or written communication.

- 6.1 Bone marrow Bx and aspirate with cytogenetics, and chimerism studies.
- 6.2 History and physical examination with evaluation of adverse events including GVHD
- 6.3 CBC, differential, platelets
- 6.4 SGPT, calcium, glucose, uric acid, magnesium, LFT, serum bilirubin, BUN and creatinine, serum protein, albumin, alkaline phosphatase, electrolytes.
- 6.5 Peripheral blood for chimerism studies.(the first chimerism study will be done 3-4 weeks post transplant).

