7.0 Criteria for Study Evaluation

7.1 Primary end point:

Deaths not attributable to the disease recurrence will be considered as an event for assessment of non-relapse mortality.

7.2 Secondary end points:

Engraftment is defined as a sustained ANC $\geq 0.5 \times 10^9/L$ for 3 consecutive days and evidence of donor chimerism by D+28 (the first chimerism study will be done 3-4 weeks post transplant).

Primary Graft Failure is defined as failure to achieve an ANC $\geq 0.5 \times 10^9/L$ for 3 consecutive days by day 28, with <10% cellularity on bone marrow biopsy and no evidence of donor chimerism.

Secondary graft failure is defined as a sustained declined of ANC $<0.5 \times 10^9/L$ for 3 consecutive days after initial documented engraftment with no evidence of disease progression.

Complete remission is defined as per response criteria defined by European Myelofibrosis network. (appendix)

Relapse will be recorded by the day of detection.

Progression free survival is defined as the interval between day of transplant and day of death or disease progression.

Overall Survival is defined as the interval between day of transplant and day of death.

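### Kaplan-Meier is planned for time to engraftment and complete remission, which death rules out, with no competing-risk method or rule for deaths before the event

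*Combined protocol and SAP*

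**What the plan says.** Section 8.0, under Secondary Endpoints, names four efficacy endpoints to be evaluated after three years of follow-up: time to engraftment, CR, PFS and OS. One method covers all four: "We will estimate each of these efficacy endpoints with the Kaplan-Meier estimators". Intervals follow: "In addition, we will report each of the estimates along with their corresponding two-sided 95% confidence intervals". Response appears once more, in a covariate analysis: "We will use logistic regression to assess the association between clinical response (CR/PR vs. SD/PD) and the same covariates".

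Section 7.2 defines the endpoints. For PFS, "Progression free survival is defined as the interval between day of transplant and day of death or disease progression", and OS runs to death, so death is an event in both. Engraftment is a neutrophil and donor-chimerism criterion to be met by day 28. CR follows an external set of response criteria. Neither includes death.

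Section 8.0 also says of this population: "The major reason for treatment failure in these patients is transplant related mortality". The document mentions cumulative incidence only when it describes NRM in earlier studies, and never as a method for this trial. It gives no rule for a patient who dies before engraftment or before CR.

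**The concern.** Kaplan-Meier treats a censored patient as someone who could still have the event later, at the same rate as those still followed. A patient who has died cannot engraft or reach CR. If deaths are censored, their place is in effect shared out among the survivors. One minus the Kaplan-Meier curve then estimates what would happen if nobody died first, which is not the share of transplanted patients who reach the endpoint.

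The second is what readers of a transplant report will take the CR figure to be. At stake are a CR percentage, and to a lesser degree an engraftment percentage, that read too high, with intervals that cover the true share less often than 95%. Enrolling more patients does not reduce the bias.

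A related route is in Section 9.0, item 5, which takes patients with primary engraftment failure off study. If they are censored at that point, the same overstatement arises again for both endpoints.

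**Working it through.** The plan gives no expected CR or engraftment rate and no estimate of either, so there is no figure of its own to reproduce. The check compares one minus Kaplan-Meier, with deaths censored, against the true cumulative incidence.

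**Inputs from the documents**
- Three-year mortality M = 15-16%. Section 2.3 says of the two reduced-intensity series: "a non-relapse mortality of 10%-16% and 3 year overall survival of 84%-85% was reported". Both are retrospective, with 21 patients each and median follow-up of 31 and 22 months (Table 1).
- Day-100 mortality of 2/45 = 4.4%, from "43/45 evaluable patients to date did not experience NRM" (Section 8.0). This counts NRM only.
- Marrow assessments "should be done around 1, 3, 6, 9, 12, 18 and 24 months post transplantation" (Section 6.0), so the last scheduled marrow is at month 24.
- Sample size n = 110; horizon 36 months.

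**Assumptions, not in the documents**
- True CR share C = 40-60%.
- Same death hazard before and after CR.
- Constant CR hazard λ up to month T, then zero.

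**Formulas, constant death hazard**
- μ = -ln(1-M)/36
- Cumulative incidence = λ/(λ+μ) × [1 - exp(-(λ+μ)T)]; solve for the λ that makes this equal C.
- One minus Kaplan-Meier at its limit = 1 - exp(-λT)

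**Worked case:** M = 0.15, T = 24, C = 0.60.
- μ = -ln(0.85)/36 = 0.00451 per month; solving gives λ = 0.04115.
- Check: 0.04115/0.04566 × [1 - exp(-0.04566 × 24)] = 0.901 × 0.666 = 0.600.
- 1 - exp(-0.04115 × 24) = 0.628, so the overstatement is 2.8 points.

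For the second column below, the death hazard is higher up to day 100 (3.29 months): -ln(43/45)/3.29 = 0.0138 per month. For M = 0.15 the later hazard is [0.1625 - 0.0455]/32.71 = 0.0036 per month.

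**Overstatement of CR, in percentage points (M 15-16%, C 40-60%)**

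| New CRs possible until | Constant death hazard | Day-100 mortality 2/45 |
|---|---|---|
| Month 12 | +1.0 to +1.5 | +1.9 to +2.8 |
| Month 24 (last scheduled marrow) | +2.0 to +3.0 | +2.9 to +4.2 |
| Month 36 (sensitivity case) | +3.0 to +4.4 | +3.7 to +5.5 |

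If CR is found only at the scheduled marrows, the figures are +2.4 to +3.6 (constant) and +3.3 to +4.8 (with 2/45). If CRs accrue uniformly to month 24 rather than at a constant hazard, they are +2.2 to +3.6 and +3.1 to +4.9.

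**Coverage of the true CR share** by the nominal 95% interval (simulated, n = 110, log-log Greenwood): with CRs to month 24, 90-92% (constant) and 84-90% (with 2/45). With CRs to month 36, 84-89% and 78-87%. An exact interval on the three-year proportion covers 95-96% throughout.

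**Scale against sampling error:** the interval half-width is 1.96 × √[C(1-C)/110] = 9.2 to 9.3 points.

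**Higher early mortality:** in a separate visit-based model (CR found at months 1, 3, 6, 9 and 12, deaths mostly early, C = 40-60%), 16% dying before CR gives +6.5 to +10.3 points and 30% gives +14.6 to +24.0.

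**Engraftment** (assumed uniform over days 10-28, n = 110): if the 2/45 deaths are spread evenly to day 100, 4.4% × 28/100 = 1.2%. That is about one death in 110 and +0.8 to +0.9 points. If all 4.4% (five deaths) fall within the first 28 days, the figure is +3.9 to +4.5.

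**Zero case:** if patients who die without the event stay in the risk set to the end of follow-up, one minus Kaplan-Meier equals the cumulative incidence.

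**The case against.** The best defence is that the bias depends on a step the plan does not state. Section 8.0 has no censoring rule, and an analyst who keeps deceased patients at risk to the end of follow-up gets the right answer. That stands as a limit on the claim: what the documents show is unspecified handling of death, and the overstatement follows only under the usual censoring. It does not excuse the gap, because nothing in the plan directs the unusual choice.

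It can also be said that little hangs on this. The estimates are descriptive secondary ones, no test or decision uses them, observed day-100 NRM is low, and in the low-mortality cases the bias is below the interval half-width of about 9 points. All of that stands, and it keeps the point modest.

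A third defence is that the logistic regression treats response as binary, so a plain proportion is implied. That does not stand. The model serves covariate association only, its four response categories have no place for a patient who dies before assessment, and the plan does not promise to report a proportion.

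A reader might go further and infer that CR will be overstated by a known amount, or by as much as 5.5 points or more. The documents do not support that. They give no CR rate or timing. The 5.5 figure needs new CRs up to month 36, although after month 24 follow-up may be only an annual visit, call or letter. The largest figures above assume far more early death than the 2/45 observed.

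**Conclusion.** The concern holds in conditional form. Kaplan-Meier is the wrong default for time to engraftment and CR, and the plan leaves death before either event unaddressed. If those deaths are censored, both shares are overstated and their intervals cover less than 95%. The direction is certain whenever deaths precede later events; the size is not fixed by the documents.

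As a low-mortality illustration and not a bound, CR is overstated by about 2 to 3 points with a constant death hazard, and by about 3 to 4 when day-100 mortality is set to 2/45. This rests on CR of 40-60%, three-year mortality of 15-16%, equal death hazard before and after CR, and a constant CR hazard to month 24. Allowing CRs to month 36 gives up to 5.5 points as a sensitivity case, and higher early mortality gives more. Engraftment moves by about 1 point.

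Nothing here touches the primary endpoint, the stopping rule, or the use of Kaplan-Meier for PFS and OS. It should be corrected because the remedy is simple, not because a conclusion of the trial is in danger.

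**What to change.** Amend the Secondary Endpoints text of Section 8.0 as follows.

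- Estimate time to engraftment and CR by cumulative incidence (Aalen-Johansen) with matching 95% confidence intervals, taking death without the event as the competing event.
- Where follow-up is complete, fixed-time proportions of all transplanted patients with exact intervals serve equally: day 28 for engraftment and a stated time for CR, with earlier deaths counted as non-events.
- Count patients removed for primary engraftment failure as not engrafted. For CR, count them as non-responders or as having a competing event, and state which. Do not censor them in either analysis.
- Keep Kaplan-Meier for PFS and OS.

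The cost is a few sentences and a little more analysis work. No new data, visits or patients are needed, since dates of death are already required for OS. The reported CR and engraftment figures will be slightly less favourable than under censoring.
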